8 STATISTICAL CONSIDERATIONS

8.1 Sample Size Determination

The primary objectives of this study are to compare OS between treatment groups, in all randomized participants and randomized participants with PD-L1 CPS ≥ 20 . OS will be compared at the 0.025 alpha level for each of the above two populations.

The OS comparison in all randomized participants will require up to 741 deaths. This number of events ensures that a two-sided, $\alpha = 0.025$ group sequential test using the O'Brien and Fleming spending function and with an interim analysis after approximately 80% of events will have overall 97% power for a HR of 1.2 for the first 7 months and 0.55 thereafter.

Delayed separation of KM curves is included in the alternative hypotheses for OS because it was observed in CA209141, a randomized phase 3 study of nivolumab versus investigator's choice therapy in platinum-refractory, recurrent/metastatic SCCHN,³⁵ and in KEYNOTE-048, a randomized phase 3 study of pembrolizumab or pembrolizumab with chemotherapy versus cetuximab with chemotherapy in untreated recurrent/metastatic SCCHN.⁵⁵

The final analysis of OS in all randomized participants is projected to occur 51 months after the first patient was randomized. An interim analysis in this population will be performed when approximately 593 deaths occur, or all randomized participants have been followed up for at least 12 months, whichever is later. It is projected for 39 months after the first patient was randomized.

Power for OS comparisons in randomized participants with PD-L1 CPS ≥ 20

At the same time as the OS analysis is done for all randomized participants, OS will also be compared between arms in the randomized participants with PD-L1 CPS ≥ 20 via a two-sided, $\alpha = 0.025$ group sequential test procedure incorporating the O'Brien and Fleming alpha spending function. The group sequential test would have an interim analysis and the final analysis of OS, at which approximately 298 and 372 deaths, respectively, are expected. With this many events, the test procedure would have an overall 99% power if the HR was 1.06 for the first 7 months and 0.45 thereafter. Table 8.1-1 summarizes the statistical assumption and power calculation.

Table 8.1-1: Statistical Assumption and Power Calculation

Primary endpoints	OS for ITT (N = 930)	OS for PD-L1 CPS ≥ 20 (N = 465)
Median OS months (N+I/EXTREME regimen)	13/10.8	14.9/10.8
Average hazard ratio	0.74	0.61
Alpha level (IA/FA)	0.01/0.022	0.01/0.022
Event Number (IA/FA)	593/741	298/372
Critical hazard ratio (IA/FA)	0.81/0.845	0.74/0.788
Power (IA/FA)	66%/97%	87%/99%
Estimated time of LPLV (IA/FA)	39/51 months	39/51 months

All sample size and power calculations were done using EAST 6.4.1.

8.2 Populations for Analyses

- All Enrolled Participants: All participants who signed an informed consent form and were registered into the IVRS.

- All Randomized Participants: All enrolled participants who were randomized to either treatment arm.
- All Randomized PD-L1 CPS ≥ 20 Participants: All randomized participants with PD-L1 CPS ≥ 20
- All Randomized PD-L1 CPS ≥ 1 Participants: All randomized participants with PD-L1 CPS ≥ 1 .
- All Treated Participants: All participants who received at least one dose of nivolumab, ipilimumab, cetuximab, cisplatin, carboplatin or 5-FU.
- Treated Participants with PD-L1 CPS ≥ 20 : All participants who received at least one dose of nivolumab, ipilimumab, cetuximab, cisplatin, carboplatin or 5-FU and have PD-L1 CPS ≥ 20 at baseline.
- All PK Participants: All participants with available serum time-concentration data
- Immunogenicity Evaluable Participants:
 - Nivolumab ADA Evaluable Participants: all treated participants with baseline and at least 1 post-baseline pre-infusion nivolumab immunogenicity assessment.
 - Ipilimumab ADA Evaluable Participants: all treated participants with baseline and at least 1 post-baseline pre-infusion ipilimumab immunogenicity assessment.
- All PD-L1 Tested participants: All participants, randomized or not, who had a tumor biopsy specimen available for tumor cell expression testing. This includes both randomized and screen failure participants.

Key analyses of study conduct, demographics, and efficacy will be done on the all randomized population and repeated on the randomized PD-L1 CPS ≥ 20 population. Participants in these analyses will be grouped as assigned at randomization.

Key analyses of exposure and safety will be done on the all treated population and repeated on the treated PD-L1 CPS ≥ 20 population. Participants in these analyses will be grouped by treatment received rather than treatment assigned at randomization. (Treatment arm received will be equal to treatment arm as randomized, unless the participant received the non-assigned regimen for all doses.)

8.3 Endpoints

8.3.1 Primary Endpoints

- OS in randomized participants with PD-L1 CPS ≥ 20
- OS in all randomized participants

OS is defined as the time between randomization and death. For participants without documentation of death, OS will be censored on the last date the participant was known to be alive.

8.3.2 Secondary Endpoints

Overall survival (OS) in randomized participants with PD-L1 CPS ≥ 1 . OS is defined the same way as for the primary endpoints.

PFS is defined as the time from randomization to disease progression, using RECIST 1.1 criteria, or, if there is no documented progression, death. (The date of progression will be based on the BICR assessment of progression). Participants who neither progress nor die will be censored on the date of their last tumor assessment. Participants who receive subsequent anti-cancer therapy prior to documented progression, including tumor-directed radiotherapy and tumor-directed surgery, will have their PFS time censored on the date of their last tumor assessment prior to subsequent therapy.

The Objective Response Rate (ORR) is defined as the number of participants with a best overall response (BOR) of complete response (CR) or partial response (PR), divided by the number randomized in the population.

The BOR is defined as the best response, based on RECIST 1.1 criteria, recorded between randomization and either progression or subsequent anticancer therapy (including tumor-directed radiotherapy and tumor-directed surgery), whichever occurs first. (The BOR will be based on BICR assessments). For participants without evidence of RECIST 1.1 progression or subsequent anticancer therapy, all available tumor evaluations will contribute to the BOR assessment.

Duration of objective response (DOR) is the time between the first documented response (CR or PR) and progression, per RECIST 1.1, or, if no progression is reported, death. The DOR of a participant who neither progresses nor dies will be censored as in the primary definition of PFS. DOR is calculated on the subset of participants whose best response was either CR or PR, according to BICR assessments.

8.3.3 Exploratory Endpoint(s)

Overall survival (OS) in randomized participants with tumor cell PD-L1 < 1%, or PD-L1 CPS of < 20, or tumor inflammation score measured as GEP \geq 10, or tumor mutation burden (TMB) \geq 7 is defined the same way as for the primary endpoints.

PFS, ORR, and DOR in randomized participants with tumor cell PD-L1 < 1%, or CPS of <20, or tumor inflammation score measured as GEP \geq 10, or tumor mutation burden (TMB) \geq 7 is defined the same way as for the secondary endpoints.

ORR and DOR in subpopulation based on selected biomarkers are defined the same way as in the secondary endpoints. Time to Objective Response (TTR) is defined as the time from randomization to the first documented response (CR or PR).

Safety and tolerability will be measured by the incidence of deaths, adverse events, serious adverse events, adverse events leading to discontinuation, immune-mediated adverse events, select adverse events, adverse events leading to dose delay, and specific laboratory abnormalities (worst grade) in each treatment group. Toxicities will be graded using the National Cancer Institute (NCI) Common Terminology Criteria for Adverse Events (CTCAE) version 4.0.

Tumor cell PD-L1 expression is defined as the percent of tumor cell membrane staining in a minimum of 100 evaluable tumor cells per validated Dako PD-L1 IHC assay. Participant's PD-L1 expression status using \geq 1% expression level will be determined prior to randomization:

- Tumor cell PD-L1 expressing ($\geq 1\%$ tumor cell membrane staining in a minimum of a hundred evaluable tumor cells)
- Tumor cell PD-L1 non-expressing ($< 1\%$ tumor cell membrane staining in a minimum of a hundred evaluable tumor cells)
- Tumor cell PD-L1 non-evaluable

Time to symptom deterioration (TTSD) is defined as the time from randomization to a clinically meaningful decline from baseline in the FHNSI-10 score. A clinically meaningful decline will be defined as a reduction of FHNSI-10 score ≥ 3 points.⁵⁶ Subjects who die without a reported deterioration will be considered to have deteriorated on the date of their death. Those who neither deteriorate nor die will be censored at the time of their last FHNSI-10 assessment.

Serum concentration will be used to characterize the PK of nivolumab and ipilimumab using a population PK approach.

Other exploratory endpoints are discussed in detail in the statistical analysis plan

8.4 Analyses

8.4.1 Demographics and Baseline Characteristics

Demographics and baseline characteristics will be summarized by treatment arm as randomized using descriptive statistics. These analyses will be done PD-L1 CPS ≥ 20 population and on the all randomized population.

8.4.2 Efficacy Analyses

[figure not shown]
Efficacy analyses will be performed using all randomized participants by treatment group as randomized.

8.4.2.1 Analysis Methods for Primary Endpoints

OS will be compared between arms via a two-sided, overall alpha = 0.025, group sequential log-rank test for each of the two primary endpoints population. The significance levels may be updated through graphical approach where the family-wise error rate will be protected in the strong sense.

Rules for updating significance levels following the Bonferroni-based graphic approach by Maurer and Bretz (2013) will be detailed in the SAP. [Figure 8.4.2.1-1](#): is the graphic display of the testing hierarchy for the endpoints to be tested in this study. The numbers next to the arrows indicate the fraction of alpha that could be passed from the source endpoint to the target endpoint if the source endpoint is statistically significant.

Figure 8.4.2.1-1: testing hierarchy for the endpoints

The nominal significance levels for each look of the group sequential log-rank test will be determined by the alpha spending function with the O’Brien and Fleming boundary based on the actual number of events observed at the time of the analysis. These tests will be stratified by the stratification factors used in the randomization.

An estimate of the hazard ratio (HR) and a corresponding two sided $100 \times (1 - \text{adjusted } \alpha)\%$ confidence interval for the HR will be generated for each endpoint using a stratified Cox proportional hazards model with treatment arm as the sole covariate. The stratification factors will be the same as those used for testing. The level for the confidence interval for the OS hazard ratio will be based on the same nominal significance level for the group sequential log-rank test.

Survival distributions will be estimated, by arm, via the Kaplan-Meier (KM) product-limit method. Median survival times along with 95% confidence intervals for the medians, will also be presented. The confidence interval for the median will be constructed using a generalization of the Brookmeyer and Crowley method based on a $\log \{-\log\}$ transformation of the survival function.⁵⁷

Greater detail on the analyses of primary endpoints, including sensitivity analyses of OS, will be provided in the statistical analysis plan.

8.4.2.2 Analysis Methods for Secondary Endpoints

The analyses of OS in the randomized participants with PD-L1 CPS ≥ 1 population will be similar to those in the randomized participants with PD-L1 CPS ≥ 20 , except that testing will be contingent upon a significant result for the primary OS comparison in PD-L1 CPS ≥ 20 population. On the other hand, if the test for this secondary endpoint is significant and the initial test for OS in all randomized participants is not significant, the latter can be retested with full $\alpha = 0.05$.

The analysis of PFS in the participants with PD-L1 CPS ≥ 20 and in all randomized participants will be performed using a stratified Cox proportional hazards model with treatment arm as the sole covariate. An estimate of the hazard ratio (HR) and a corresponding two sided 95% CI for the HR will be generated. Survival distributions will be estimated, by arm, via the Kaplan-Meier (KM)

product-limit method. Median survival times along with 95% CI for the medians, will also be presented. The confidence interval for the median will be constructed using a generalization of the Brookmeyer and Crowley method based on a log $\{-\log\}$ transformation of the survival function. No statistical test will be performed.

ORR and its associated 95% CI will be presented per arm, in all randomized participants and participants with PD-L1 CPS ≥ 20 . The confidence interval for ORR will be computed using the Clopper and Pearson method. The odds ratio (OR) and 95% confidence interval for the ratio will be generated using the Cochran-Mantel-Haenszel (CMH) method.

The distribution of DOR will be estimated via the KM method for participants whose best response is PR or CR, by arm. Medians and 6, 9, and 12 month rates will also be estimated. These analyses will be conducted on the all randomized population and PD-L1 CPS ≥ 20 subpopulation.

No statistical test will be performed for ORR, DOR for all randomized participants and participants with PD-L1 CPS ≥ 20 .

8.4.3 Safety Analyses

Safety analyses are restricted to treated participants. Descriptive statistics of safety will be presented using the National Cancer Institute (NCI) Common Terminology Criteria for Adverse Events (CTCAE) version 4.0 by treatment arm. All AEs, drug-related AEs, SAEs and drug-related SAEs will be tabulated using the worst grade per NCI CTCAE v 4.0 criteria by system organ class and preferred term. On-study lab parameters including hematology, coagulation, chemistry, liver function and renal function will be summarized using worse grade per NCI CCAE v 4.0 criteria. These analyses will be performed on both the population of treated participants with PD-L1 expressing tumors and on all treated participants.

8.4.4 Pharmacokinetic Analyses

The nivolumab and ipilimumab concentration data obtained in this study may be combined with data from other studies in the clinical development program to develop or refine a population PK model. This model may be used to evaluate the effects of intrinsic and extrinsic covariates on the PK of nivolumab and to determine measures of individual exposure (such as steady-state peak, trough, and time-averaged concentration). In addition, model determined exposures may be used for exposure-response analyses. Results of population PK and exposure response-analyses will be reported separately.

8.4.5 Biomarker Analyses

Analyses of PD-L1 expression will include:

- KM Plots of efficacy by arm for each PD-L1 CPS status subset (analyses with PD-L1 CPS cutoff of ≥ 20 , ≥ 1 , < 20 , and other exploratory cut-points). This analysis will include HRs of the experimental to control arm within subset and corresponding 95% CI.
- KM Plots of PFS and OS by arm for each tumor cell PD-L1 status subset ($< 1\%$, $\geq 1\%$, unknown). (Similar analyses with 5%, 10%, 50%, other exploratory PD-L1 cutoffs will be conducted). This analysis will include HRs of the experimental to control arm within subset and corresponding 95% CI.

- Box plots of PD-L1 expression at baseline versus response status, by treatment group
- Odds ratios for tumor response of the experimental to the control arm by PD-L1 status subset and corresponding 95% CI
- Model-based assessment of the interaction between treatment and PD-L1 status for PFS, OS, and ORR.

The analyses of tumor mutational burden (TMB) and tumor inflammation gene expression profile (GEP) will also include KM plots by TMB and GEP subgroups, box plots of TMB by response, and model based assessments of interaction between treatment and TMB/GEP for PFS, OS, and ORR.

Associations between other potential biomarkers and efficacy and safety may be investigated as well. These analyses will be completed with biomarkers measured in blood and in tumor samples and will focus primarily on SNPs in select genes associated with immunity or on the expression of PD-1 and PD-L2 proteins in tumor specimens. Similar analyses may be completed with data regarding serum-soluble factors, serum miRNA content, T-cell populations, and putative additional analyses to be completed using FFPET. Associations between biomarkers and efficacy measures will be analyzed on all randomized participants with available biomarker data. Efficacy measures will include response, PFS, and OS. Demographic and case-history factors will be examined to determine whether stratification or adjustments should be made within the subsequent statistical analyses, and if necessary, the appropriate stratification or adjustment will be made. Biomarkers will be summarized graphically as they relate to efficacy and safety endpoints, as applicable. Summary statistics may be tabulated. SNP allele frequencies may be summarized. The relationships between binary measures (eg. response) and candidate biomarkers will be investigated using logistic regression. Associations may be summarized in terms of point and interval estimates of hazard ratios, odds ratios, or other statistics, as appropriate for the analyses completed. Models to predict clinical activity based on combinations of biomarkers may also be investigated. Additional post hoc statistical analyses not specified in the protocol, such as alternative modeling approaches may be completed. All analyses described above are based on the availability of the data.

8.4.6 Outcomes Research Analyses

Exploratory analyses of EQ-5D and FACT-H&N (including FHNSI-10) data will be performed in randomized participants who have an assessment at baseline (Day 1, assessment prior to administration of drug on day of first dose) and at least 1 subsequent assessment while on treatment. Questionnaire completion rate, defined as the proportion of questionnaires actually received out of the expected number, will be calculated and summarized at each assessment point.

EQ-5D data will be described by treatment group as randomized in the following ways:

- EQ-5D index scores and post-baseline changes in scores will be summarized at each assessment time point using descriptive statistics (ie, N, mean with SD and 95% CI, median, first and third quartiles, minimum, maximum). In the base case, scores will be calculated using the UK preference-weighting algorithm.

- EQ-5D VAS scores and post-baseline changes in scores will be summarized at each assessment time point using descriptive statistics (ie, N, mean with SD and 95% CI, median, first and third quartiles, minimum, maximum).
- The proportion (N) of participants reporting no, moderate, or extreme problems will be presented for each of the 5 EQ-5D dimensions at each assessment time point. Participants with missing data will be excluded from the analysis.
- A by-participant listing of the level of problems in each dimension, corresponding EQ-5D health state (ie, 5-digit vector), EQ-5D index score, and EQ-5D VAS score will be provided.

FACT-H&N data collected during on-study clinic visits and at follow up visits 1 and 2 will be described by treatment group as randomized in the following ways:

- Scores and post-baseline changes in scores for the following components of the FACT-H&N will be summarized at each assessment time point using descriptive statistics (ie, N, mean with SD and 95% CI, median, first and third quartiles, minimum, maximum): FACT-G, PWB, SWB, EWB, FWB, HNC, FHNSI-10, FACT-H&N TOI, FACT-H&N total, and individual FACT-H&N items.

FHNSI-10 data will be described by treatment group as randomized in the following ways:

- Scores and post-baseline changes in scores will be summarized at each assessment time point (i.e., first, second, third, etc. survival follow-up visit recognizing that the timing of visits will vary among participants) using descriptive statistics (ie, N, mean with SD and 95% CI, median, first and third quartiles, minimum, maximum).
- The proportion (N) of participants with symptomatic deterioration, defined as a clinically meaningful decline in score (worsening from baseline ≥ 3 points) or death, will be summarized at each assessment time point (ie, first, second, third, etc. survival follow-up visit recognizing that the timing of visits will vary among participants).
- Time to symptom deterioration (TTSD) will be estimated using the KM product-limit method, by arm as randomized. Two-sided 95% confidence intervals for median TTSD will be computed.

Analyses of patient-reported outcomes will be performed on both the randomized PD-L1 CPS ≥ 20 population and the all randomized population.

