Pregnancy Test (WOCBP only)	X	Serum or urine within 24 hours prior to first dose and then every 4 weeks (\pm 1 week) regardless of dosing schedule.
Concomitant Medications	X	
Efficacy Assessments		
Tumor Assessment	X	
 • Tumor assessments should occur every 6 weeks (starting from first dose \pm 1 week) for the first 48 weeks, then every 12 weeks (\pm 1 week) until disease progression or treatment is discontinued, whichever occurs later. If treatment beyond progression is approved, then scanning should continue every 6 weeks \pm 1 week until further progression is determined. • CT or MRI of the neck, chest, abdomen, pelvis and all known sites of disease. Use same imaging method as was used at screening/baseline.

Table 5.1-2: On Treatment Procedural Outline (All Treatments) CA209651 (All Cohorts)

Procedure	During Treatment Visit ^{a,b}	Notes
		
 MRI of the brain (without AND with Gadolinium contrast) is required for participants with a history of brain metastasis. Note: MRI of the brain is preferred but CT scan is a participant acceptable. 
Surveillance scans should be performed approximately every 12 weeks, or sooner if clinically indicated. (CT of the head without AND with contrast may be performed if MRI is contraindicated).

Outcomes Research Assessment		
FACT-H&N	X	
Assessed following randomization but before treatment every 6 weeks (\pm 1 week) regardless of dosing.
 
Can be collected over the phone at regularly scheduled time if needed.

EQ-5D-3L	X	
Assessed following randomization but before treatment every 6 weeks (\pm 1 week) regardless of dosing.
 
Can be collected over the phone at regularly scheduled time if needed.

Health care resource utilization questions	X	To be completed by the site in CRF
Pharmacokinetic Assessments		
PK samples (Arm A Only)	X	See Table 5.5-1.
Immunogenicity blood samples	X	See Table 5.5-1.
Biomarker Assessments		
Serum sample: Soluble Biomarkers	X	See Table 5.6-1.
Whole Blood sample: SNP (pre dose D1 only) & Gene expression	X	See Table 5.6-1
Plasma samples	X	See Table 5.6-1

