#### 4.3.7 Time to Disease-related Symptom Deterioration

Time to disease-related symptom deterioration (TTSD) is defined as the time from randomization to a clinically meaningful decline from baseline FHNSI-10 score (worsening from baseline  $\geq 3$  points).

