#### 7.9 Clinical Outcomes Assessments

The outcome research analyses will be performed using all randomized subjects at the time of final analysis of OS.

The analyses of EQ-5D-3L and FACT-HN outcomes will be restricted to all randomized subjects and the randomized subjects with PD-L1 CPS  $\geq$  20 who have an assessment at baseline and at least one post-baseline assessment.

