#### 7.9.1 EQ-5D-3L

The following descriptive analyses will be conducted:

- EQ-5D-3L questionnaire completion rate, defined as the proportion of questionnaires actually received out of the expected number (i.e. number of subjects on treatment or in follow up), will be calculated and summarized for each assessment time point by treatment group.
- A by-subject listing of the level of problems in each dimension, corresponding to EQ-5D-3L health state (i.e., 5-digit vector), EQ-5D-3L utility index score, and EQ-5D-3L VAS score will be provided.
- Proportion of subjects reporting problems for the 5 EQ-5D-3L dimensions at each assessment time point will be summarized by level of problem and by treatment group. Percentages will be based on number of subjects assessed at assessment time point. Separate analyses will be performed including or excluding cases with missing data
- For the EQ-5D-3L utility index and VAS scores, separately:
  - Mean score and mean change from baseline at each assessment time point will be summarized by treatment group using descriptive statistics (N, mean with SD and 95% CI, median, first and third quartiles, minimum, maximum).
  - A line graph summarizing the mean changes from baseline will be produced.

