#### 7.9.2 FACT-HN

FACT-HN data will be described by treatment group as randomized in the following ways:

- Scores and post-baseline changes in scores for the following components of the FACT-HN will be summarized at each assessment time point using descriptive statistics (ie, N, mean with SD and 95% CI, median, first and third quartiles, minimum, maximum): FACT-G, PWB, SWB, EWB, FWB, HNC, FHNSI-10, FACT-HN TOI, and FACT-HN total.
- A line graph summarizing the mean changes from baseline will be produced.
- The proportion (N) of subjects with symptomatic deterioration, defined as a clinically meaningful decline in FHNSI-10 score (worsening from baseline ≥ 3 points), will be summarized at each assessment time point.
- TTSD will be estimated using the Kaplan-Meier (KM) product limit method and will be displayed graphically. A table will be produced presenting number of events, number of subjects involved, medians, and 95% CIs for the medians. Median values of TTSD, along with two-sided 95% CI in each treatment group will be computed based on a log-log transformation method.
- The proportion (N) of subjects with symptomatic deterioration, defined as a clinically meaningful decline in FHNSI-10 score (worsening from baseline ≥ 3 points), or death, will be summarized at each assessment time point.
- Time to symptomatic deterioration or death will be estimated using the Kaplan-Meier (KM) product limit method and will be displayed graphically. A table will be produced presenting number of events, number of subjects involved, medians, and 95% CIs for the medians. Median values of time to symptomatic deterioration or death, along with two-sided 95% CI in each treatment group will be computed based on a log-log transformation method.

- Proportion (N) of subjects endorsing each response option for item GP5, "I am bothered by side effects of treatment," will be summarized by treatment group at each assessment time point. Separate analyses will be performed including or excluding cases with missing data.
- Proportion (N) of subjects with post-baseline improvement, stability, or worsening in GP5 item response will be summarized by treatment group at each assessment time point (except baseline). Separate analyses will be performed including or excluding cases with missing data.

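### Time to symptom deterioration counts death as an event, but the analysis set drops anyone who dies before a post-baseline questionnaire, and protocol and SAP differ on both the death rule and the set

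*Protocol*

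**What the plan says.** **Event definition.** Protocol 8.3.3 runs TTSD from randomization to a fall of at least 3 points in FHNSI-10 and adds: "Subjects who die without a reported deterioration will be considered to have deteriorated on the date of their death". Protocol 8.4.6 also counts death in the deterioration proportion ("or death, will be summarized at each assessment time point"). SAP 4.3.7 has no death rule and no censoring rule; its TTSD "is defined as the time from randomization to a clinically meaningful decline from baseline FHNSI-10 score". SAP 7.9.2 analyses that endpoint and, separately, a composite: "Time to symptomatic deterioration or death will be estimated using the Kaplan-Meier (KM) product limit method".

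**Analysis set.** Protocol 8.4.6 requires a baseline assessment "and at least 1 subsequent assessment while on treatment". SAP 7.9 restricts the questionnaire analyses, in all randomized subjects and in the CPS ≥ 20 subset, to those "who have an assessment at baseline and at least one post-baseline assessment".

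**Timing.** Protocol Table 5.1-2 has the FACT-H&N "Assessed following randomization but before treatment every 6 weeks" (± 1 week). SAP Table 4.3.5-1 places the first post-baseline time point at Day 43.

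**Completion rate.** SAP 7.9.1 defines the EQ-5D-3L rate as questionnaires received "out of the expected number (i.e. number of subjects on treatment or in follow up".

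**The concern.** A participant with a baseline score who dies in week 4 without completing another questionnaire has a TTSD event under protocol 8.3.3. The same participant fails the entry condition of protocol 8.4.6 and of SAP 7.9. Membership of the set therefore depends on surviving long enough to fill in a form, and death is itself part of the endpoint. The earliest events are removed from both death-inclusive measures: protocol TTSD and the SAP composite.

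Two mismatches add to this. What is called TTSD includes death in the protocol but not in the SAP. And a participant who stops treatment early and whose only later questionnaire is at Follow-up 1 is in the SAP set but not in the protocol set.

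At stake is the early part of the curve. The planning assumptions put more early deaths on nivolumab + ipilimumab (N+I), so the exclusion would tend to favour that arm. Early deaths would not show up as missing in a completion table whose denominator is subjects still on treatment or in follow-up.

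**Working it through.** The documents give no size for the questionnaire analysis set and no figure for TTSD, so there is no planned number to reproduce. The number of early deaths was estimated from the plan's own survival assumptions.

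**Inputs** (Protocol 8.1 and Table 8.1-1; SAP section 5)
- All randomized: N = 930, 1:1, so 465 per arm; median OS 13 (N+I) and 10.8 months (EXTREME); HR 1.2 to month 7, then 0.55.
- CPS ≥ 20: N = 465, assumed split 1:1; medians 14.9 and 10.8; HR 1.06 to month 7, then 0.45.
- SAP section 8: 1 month = 30.4375 days, so day 42 = 42/30.4375 = 1.38 months.

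**Two control-arm shapes (assumptions)**

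1. *Two-piece.* Control hazard a to month 7 and b afterwards, solved so that both stated medians hold. All randomized: 7a + 3.8b = ln 2 and 1.2(7a) + 0.55(6b) = ln 2, giving a = 0.0393, b = 0.1100. CPS ≥ 20: 7a + 3.8b = ln 2 and 1.06(7a) + 0.45(7.9b) = ln 2, giving a = 0.0513.
2. *Exponential.* a = ln 2/10.8 = 0.0642. With HR 1.2/0.55 this gives an N+I median of 11.4 months, not the stated 13, so it fits the plan less well.

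**Deaths by day 42:** 1 − exp(−a × 1.38) for EXTREME; the same with a multiplied by the early HR for N+I.

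| Population, curve | EXTREME | N+I | Total | N+I excess |
|---|---|---|---|---|
| All randomized, two-piece | 0.0528 × 465 = 24.5 | 0.0630 × 465 = 29.3 | 53.8 | 4.8 |
| All randomized, exponential | 0.0848 × 465 = 39.4 | 0.1008 × 465 = 46.9 | 86.3 | 7.5 |
| CPS ≥ 20, two-piece | 15.9 | 16.8 | 32.7 | 0.9 |
| CPS ≥ 20, exponential | 19.7 | 20.8 | 40.5 | 1.1 |

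Moving the cut-off across the ± 1 week window (day 36 to day 50) gives all-randomized totals of 46 (two-piece, day 36) to 102 (exponential, day 50). Treating the two counts as independent binomials, N+I has the larger count in about 72% (two-piece) to 78% (exponential) of trials. In CPS ≥ 20 the figure is 53% to 54%.

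**Effect on the early curve.** Taking deaths alone, the proportion with an event by month 3 is 1 − exp(−3h) in everyone and 1 − exp(−1.62h) among survivors to day 42 (3 − 1.38 = 1.62), with h = a for EXTREME and 1.2a for N+I. All randomized, two-piece:
- everyone: 11.1% EXTREME, 13.2% N+I, difference 2.1 points;
- survivors to day 42: 6.2% and 7.4%, difference 1.2 points.

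With the exponential curve the difference falls from 3.1 to 1.9 points.

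**The case against.** **Low consequence.** TTSD is an exploratory objective, estimated by Kaplan-Meier by arm with no test. This stands and limits how much weight the point carries.

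**Broader population statements.** Protocol 8.4.6 closes by saying these analyses use the randomized and CPS ≥ 20 populations, with no questionnaire condition. That does not override the restriction: SAP 7.9 attaches the condition to those same two populations. At best the protocol section is inconsistent with itself.

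**The SAP already has a death-inclusive version.** True, and it was added in SAP version 2.0. The death-rule mismatch is therefore partly one of labelling. But the composite uses the same restricted set and loses the same early deaths.

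**The exclusion is visible.** SAP 7.9.2 reports the number of subjects involved, and deaths are tabulated elsewhere. A reader could see a shortfall, but that does not correct the curve.

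**Day 42 is not a hard limit.** SAP Table 4.3.5-1 accepts a questionnaire from Day 2, and Follow-up 1 falls 30 days after the last dose. Some early deaths will have qualified. This stands.

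**The early hazard may be lower.** Eligibility requires a life expectancy of at least 3 months. At half and a quarter of the exponential hazard, deaths by day 42 fall from 86 to 44 and 22. In addition, assuming uniform 26-month accrual and no dropout, the two-piece curve predicts about 753 and 857 deaths at months 39 and 51, and the exponential about 688 and 791, against the planned 593 and 741. Neither curve is validated for the first six weeks, so the counts indicate scale only.

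**Direction.** The expected tilt applies a seven-month planning HR uniformly to the first six weeks and covers deaths only. Early discontinuation and non-completion also shape the set and could act either way. This too stands.

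**Conclusion.** The concern holds. Followed as written, the plan gives death-inclusive curves from which the earliest deaths have been removed, and the two documents disagree on what TTSD is and on who is analysed.

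The size is at most about 54 to 86 of 930 participants by day 42, and 33 to 41 of 465 in CPS ≥ 20. These are upper bounds: they assume that every early death had a baseline score and that none had completed a later questionnaire. The understatement of early event rates applies to both arms. A small relative gain for N+I is likely but not certain in all randomized participants, and close to nil in CPS ≥ 20. The month-3 figures describe deaths alone and are not estimates of the effect on TTSD. Confidence is high on the conflict between the passages and much lower on the direction of any between-arm shift. The change should be made, but nothing in the primary or secondary analyses depends on it.

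**What to change.** - Analyse TTSD and time to deterioration or death in all randomized participants with a baseline FHNSI-10 score, and in the CPS ≥ 20 subset of them.
- In the death-inclusive endpoint, count a death before the first post-baseline questionnaire as an event on its date. Censor at baseline only those alive with no later assessment.
- Use one TTSD death rule in protocol 8.3.3 and SAP 4.3.7, with the death-free version as supportive and its censoring rule stated.
- Use one analysis-set definition in protocol 8.4.6 and SAP 7.9, settling whether a later questionnaire must be on treatment where one is required.
- Keep the post-baseline requirement only for change-from-baseline summaries.
- Tabulate by arm the participants excluded for lack of a baseline score and the deaths before the first post-baseline questionnaire.

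The cost is wording in both documents and one by-arm table. No new data are needed.
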